## Study Schedule Protocol I8Z-MC-APCA

Procedure	Screen	Periods 1, 2, 3 a			FU/ET b	Comments
	Up to Day -28	Day -1	Day 1 c	Day 2		
Continuous ECG monitoring			X			15 ECGs will be extracted from the continuous ECG recording at -5, 30, 60, 120, and 180 minutes postdose for each Day 1 dose administration.
PK samples: LY3185643 or glucagon (minutes)			0 (predose), 15 ( $\pm 2.5$ ), 30 ( $\pm 2.5$ ), 60 ( $\pm 5$ ), 120 ( $\pm 10$ ), 180 ( $\pm 10$ )			Sampling times are relative to the time of each study drug administration.
Glucose samples (minutes)			-5 ( $\pm 2.5$ ), 0 (predose), 5 ( $\pm 1$ ), 10 ( $\pm 1$ ), 15 ( $\pm 2.5$ ), 22 ( $\pm 2.5$ ), 30 ( $\pm 2.5$ ), 45 ( $\pm 5$ ), 60 ( $\pm 5$ ), 75 ( $\pm 5$ ), 90 ( $\pm 5$ ), 105 ( $\pm 5$ ), 120 ( $\pm 5$ ), 150 ( $\pm 5$ ), 180 ( $\pm 5$ )			Blood concentrations using YSI glucose analyzer. Sampling times are relative to the time of each study drug administration.
PD samples: C-peptide, glucose (minutes)			-5 ( $\pm 2.5$ ), 0 (predose), 5 ( $\pm 1$ ), 15 ( $\pm 2.5$ ), 30 ( $\pm 2.5$ ), 60 ( $\pm 5$ ), 120 ( $\pm 5$ )			Sampling times are relative to the time of each study drug administration.
Immunogenicity (LY3195643 antibodies) samples			Any time before the first dose		X	Period 1 and Period 3 only. Prior to the first dose only.

Abbreviations: AE = adverse event; CRU = clinical research unit; ECG = electrocardiogram; ET = early termination; FU = follow-up; PD = pharmacodynamics; PK = pharmacokinetics.

Note: The site should schedule activities as appropriate. In cases where several study procedures are scheduled at the same time, the order of priority for these procedures will be as follows: PK samples, PD samples, vital signs, ECG, clinical laboratory samples.

a Each treatment period will consist of 3 days (Days -1 to 2). Subjects should return for the next period with a minimum of 3 days between treatment periods.

b FU/ET visit will occur at least 30 days after completing the last dose of study treatment.

c Study drug will be administered 3 times on Day 1 in each period. Day 1 activities will be performed 3 times on Day 1 with the sampling times corresponding to each study drug administration.

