## 5. Study Design

### 5.1. Overall Design

This study is a Phase 1, single-center, subject- and investigator-blind, randomized, 9-way, 3-period crossover study in healthy subjects to evaluate the PK and PD of LY3185643 and rGlucagon after SC administration.

Up to 37 healthy men and women may be enrolled to target approximately 18 subjects to complete the study. Each subject will receive 3 doses on each of 3 dosing days (total of 9 doses: 5 doses of LY3185643 and 4 doses of rGlucagon) administered SC. Doses will be administered in a 9-way complete crossover design in 3 periods, and subjects will be randomized to predefined treatment sequences. Completers are defined as subjects who have received all 9 doses.

Subjects will be required to attend the CRU on at least 5 occasions:

- 1 screening visit (may occur up to 28 days before randomization)
- 3 treatment periods
- 1 follow-up visit (at least 30 days after completing the last dose of study treatment)

Each study period will consist of 3 days (Days -1 to 2). Subjects should return for the next period with a minimum of 3 days between treatment periods.

On Day -1, subjects will be admitted to the CRU. Subjects will be provided a carbohydrate-rich meal in the evening at approximately 10:00 PM and will remain fasted until completion of the study procedures on Day 1.

On Day 1, study drug will be administered SC as follows:

- Dose 1: morning of Day 1
- Dose 2: approximately 4 hours after administration of the first dose
- Dose 3: approximately 4 hours after administration of the second dose

Blood samples will be collected for the determination of concentrations of LY3185643, glucagon, glucose, C-peptide, and for immunogenicity as shown in the Schedule of Activities (Section 2).

Safety data will include clinical examinations, vital signs, electrocardiograms (ECGs; including telemetry), clinical laboratory tests, and a record of AEs.

All study procedures will end approximately 4 hours after the third dose. Subjects will be provided dinner and stay overnight in the CRU for observation. Subjects will be discharged the following day (Day 2) after completion of all assessments as shown in the Schedule of Activities (Section 2).

Figure [APCA.5.1](#) illustrates the study design.

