### **10.3.3.2. Pharmacodynamic Statistical Inference**

PD parameters of interest may be transformed before statistical analysis if deemed necessary. Unless specified otherwise, parameters will be analyzed using a nonlinear mixed-effects model with period, treatment (LY3185643 or rGlucagon), and dose (within treatment) as fixed effects, baseline glucose as a covariate, and subject as a random effect. The use of other influencing variables as covariates will be explored as detailed in the statistical analysis plan.

A conversion factor will be defined in the model for each parameter to estimate the relative potency of LY3185643 to rGlucagon. In addition, a conversion factor will be estimated between LY3185643 and rGlucagon for multiple parameters simultaneously using a similar mixed nonlinear model approach to account for the correlation between parameters for the same subject. Model details will be discussed in the statistical analysis plan.

All PD parameters including the baseline-corrected parameters will be summarized by dose group and tabulated. Summary statistics will be provided. The individual observed and mean (by dose group) time profile of the PD measurements after dosing will be plotted.

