5. STUDY DESIGN

This study is a Phase 1, single-center, subject- and investigator-blind, randomized, 9-way, 3-period crossover study in healthy subjects to evaluate the PK and PD of LY3185643 and rGlucagon after subcutaneous (SC) administration.

Up to 27 healthy men and women may be enrolled to target approximately 18 subjects to complete the study. Each subject will receive 3 doses on each of 3 dosing days (total of 9 doses: 5 doses of LY3185643 and 4 doses of rGlucagon) administered SC. Doses will be administered in a 9-way complete crossover design in 3 periods, and subjects will be randomized to predefined treatment sequences. Completers are defined as subjects who have received all 9 doses.

Subjects will be required to attend the Clinical Research Unit (CRU) on at least 5 occasions:

- 1 screening visit (may occur up to 28 days before randomization)
- 3 treatment periods
- 1 follow-up visit (at least 30 days after completing the last dose of study treatment)

Each treatment period will consist of 3 days (Days -1 to 2). Subjects should return for the next period with a minimum of 3 days between treatment periods. On Day -1, subjects will be admitted to the CRU. Subjects will be provided a carbohydrate-rich meal in the evening at approximately 10:00 PM and will remain fasted until completion of the study procedures on Day 1. On Day 1, study drug will be administered SC as follows:

- Dose 1: morning of Day 1
- Dose 2: approximately 4 hours after administration of the first dose
- Dose 3: approximately 4 hours after administration of the second dose

Blood samples will be collected for the determination of concentrations of LY3185643, glucagon, glucose, C-peptide, and for immunogenicity as shown in the Schedule of Activities. Blood samples for measurement of glucose concentrations using YSI glucose analyzer will also be collected.

Safety data will include clinical examinations, vital signs, elec trocardiograms (ECGs; including telemetry, holter monitoring), clinical laboratory tests, concomitant medications and a record of adverse events (AEs).

All study procedures will end approximately 4 hours after the third dose. Subjects will be provided dinner and stay overnight in the CRU for observation. Subjects will be discharged the following day (Day 2) after completion of all assessments as shown in the Schedule of Activities.

Figure 1 illustrates the study design:

Period 1				Periods 2 and 3			Summary			
	Day -1	Day 1			Day 2					

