9.4.2 Pharmacodynamic Statistical Methodology

All PD parameters including the baseline-corrected parameters will be summarized by dose group and tabulated. The individual observed and mean (by dose group) time profile of the PD measurements after dosing will be plotted.

For these parameters, a linear model will be fitted to account for the PD difference between LY3185643 and rGlucagon. The model is detailed below. In addition, partial AUC for glucose over appropriate time intervals will be calculated using the trapezoidal rule. The AUC for each subject after each dose will also be baseline-adjusted. Baseline for each dose will be defined as the average of predose values for that dose.

For each PD parameter, the linear model that is proposed to account for differences between LY3185643 and rGlucagon is:

$$Y_{kl} = \beta_0 + \beta_1 d_{kl} + \beta_2 d_{kl} * Z_{kl} + u_k + e_{kl} \quad (1)$$

where k denotes the subject index, l denotes the period index, d_{kl} is the dose in mg during each period, Z_{kl} is the treatment indicator (0 for rGlucagon and 1 for LY3185643), $u_k \sim NI(0, \sigma_{u^2})$ denotes the between subject error, and $e_{kl} \sim NI(0, \sigma_{e^2})$ denotes the within-subject error. The

notation “NI” means “Normally Independent.” There is no term for the treatment group indicator Z_{kl} because at dose = 0 the response should be the same for both treatment groups. Setting the mean responses for each treatment equal to each other, it follows that:

$$\beta_0 + \beta_1 D_1 + \beta_2 D_1 = \beta_0 + \beta_1 D_0$$

where D_0 denotes the rGlucagon dose and D_1 denotes the LY3185643 dose. It follows that $D_1 = \lambda D_0$ where $\lambda = \beta_1/(\beta_1 + \beta_2)$ is the conversion factor that determines how many mg of LY3185643 are equivalent to one mg of rGlucagon. The model (1) can be reparameterized as a nonlinear mixed model:

$$Y_{kl} = \beta_0 + \beta_1 d_{kl} + (1 - \lambda)/\lambda \beta_1 d_{kl} * Z_{kl} + u_k + e_{kl}.$$

Then, the conversion factor λ (the point estimate and the 90% confidence interval) will be directly estimated from this nonlinear model. This model may be extended to allow for multiple parameter values, if deemed appropriate.

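### The PD model ignores correlation among the three profiles of a dosing day, so the conversion-factor estimate may be inefficient and its 90% CI is not assured of nominal coverage

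*SAP*

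**What the plan says.** Protocol 5.1 sets out the dosing: "Each subject will receive 3 doses on each of 3 dosing days". The Schedule of Activities repeats it: "Study drug will be administered 3 times on Day 1 in each period". Per subject, SAP section 5 gives a "total of 9 doses: 5 doses of LY3185643 and 4 doses of rGlucagon". A subject thus contributes nine PD profiles, in three groups of three.

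Model (1) in SAP 9.4.2 is Y_kl = β0 + β1 d_kl + β2 d_kl Z_kl + u_k + e_kl, "where k denotes the subject index, l denotes the period index". The covariate d_kl "is the dose in mg during each period", which implies one dose per period. The term e_kl "denotes the within-subject error", and both random terms are stated to be normal and independent. The conversion factor is λ = β1/(β1 + β2), reported with a 90% CI.

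The model in Protocol 10.3.3.2 has fixed effects for period, treatment and dose within treatment, with "baseline glucose as a covariate, and subject as a random effect". It has no subject-by-day term either. Its period effect is common to all subjects and cannot absorb one subject's good or bad day.

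**The concern.** The three profiles of a day follow one evening meal, one continuing fast and one inpatient stay, so they may resemble each other more than profiles from different days. If so, two things follow.

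- Contrasts within a day are more precise than contrasts between days, and an efficient analysis would give them more weight. In the example table, 23 of the 27 sequence-days contain both drugs, so the design does allow comparison within a day.
- The independence behind the reported standard error fails.

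The indexing problem holds whatever the correlation is, because subject and period alone do not identify a profile. Protocol 3.1 says relative potency will guide changes to the control algorithms of the artificial pancreas system, so the estimate of λ and its CI matter.

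**Working it through.** The documents state no power, CI width or variance component, so there is no planned figure to reproduce.

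**Inputs from the documents.** The example table (Protocol Table APCA.5.1, SAP Table 1), its dose key, and 18 completers.

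**Assumptions.** Two completers per sequence, giving 54 subject-days and 162 profiles; true λ = 1; a day share ρ of within-subject variance, which is set to 1. Subject variance drops out because every completer receives all nine treatments.

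**Step 1: what drives λ.** By the delta method at λ = 1 (β2 = 0), Var(λ̂) = Var(β̂2)/β1². Regress d·Z on an intercept and d, then split the residual sum of squares by stratum. In the example table 0.279 lies between days within subject and 0.721 within days. Call the first figure b.

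**Step 2: additive day effect.** The between-day stratum has variance 1 + 2ρ and the within-day stratum 1 − ρ. Up to a common factor:

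- R, the variance model (1) reports. It pools 2 between-day and 6 within-day degrees of freedom per subject: [2(1 + 2ρ) + 6(1 − ρ)]/8 = 1 − ρ/4
- T, the true variance of the same estimator: b(1 + 2ρ) + (1 − b)(1 − ρ) = 1 − ρ + 3bρ
- G, the variance with a day term: 1/[b/(1 + 2ρ) + (1 − b)/(1 − ρ)]

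| ρ | R | T | G | Variance T/G | Reported SE / SE with day term, √(R/G) | Reported SE / true SE, √(R/T) |
|---|---|---|---|---|---|---|
| 0.1 | 0.975 | 0.984 | 0.967 | 1.02 | 1.004 | 0.996 |
| 0.2 | 0.950 | 0.967 | 0.909 | 1.06 | 1.02 | 0.991 |
| 0.3 | 0.925 | 0.951 | 0.830 | 1.15 | 1.06 | 0.986 |
| 0.5 | 0.875 | 0.919 | 0.632 | 1.45 | 1.18 | 0.976 |

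Two comparisons must be kept apart. The interval from model (1) is 0.4%, 2%, 6% and 18% wider than one from a model with the day term. Measured against the sampling error of its own estimator, it is 0.4% to 2.4% too narrow, which leaves coverage at about 89% to 90%. A REML simulation of 200 trials per setting gave width ratios of 1.01 at ρ = 0.3 and 1.16 at ρ = 0.5; that is too few runs to judge coverage.

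**Step 3: dependence on the schedule.** R equals T only when b = 0.25. Relabelling the treatments in the table at random (2,000 draws) moved b between 0.16 and 0.35. At ρ = 0.3:

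- b = 0.159: T = 0.7 + 0.9 × 0.159 = 0.843, so √(0.925/0.843) = 1.05
- b = 0.351: T = 0.7 + 0.9 × 0.351 = 1.016, so √(0.925/1.016) = 0.95

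Even the sign of the SE error depends on the actual schedule.

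**Step 4: day effect on the dose slope.** Let each subject-day have its own slope, with SD at 0.2 mg of 0.5, 1 or 1.5 residual SDs (assumed). Reported SE / true SE is then 0.94, 0.84 and 0.75. Coverage, 2Φ(1.645 × ratio) − 1, is about 88%, 83% and 78%. Adding only a random intercept by subject-day gives about 88%, 84% and 79%, with CI width changing by 1.3% or less. If slopes vary between subjects but not between days, the error reverses: the ratios are 1.02, 1.07 and 1.15.

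**The case against.** The strongest reply is that little additive day effect may remain. Meal, fast and confinement are the same in every period (Protocol 6.3.1 and 5.1), which argues for a small day share. Several endpoints are changes from that dose's own predose mean, so a shift in a subject's glucose level on a given day is largely subtracted. The protocol model also carries baseline glucose. This stands for the baseline-corrected endpoints. It does not remove the point, because SAP 9.4.1 also lists uncorrected Cmax, and model (1) omits the protocol's baseline covariate. A day effect that survives baseline correction may well be one of responsiveness. That is the case in which the CI is too narrow and a random intercept alone barely helps.

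It is also fair to say that no stated precision target is missed: the sample size is justified only as customary for Phase 1.

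Three stronger readings are tempting, and the documents do not support them.

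- A reader might infer that model (1) throws within-day information away. It does not. All nine profiles enter, with weights that are at most inefficient.
- A reader might infer that the CI is always wider than it need be. That depends on what it is compared with, on the schedule and on the kind of day effect.
- A reader might turn the variance ratios into a number of extra completers. That needs a day share that neither document gives.

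**Conclusion.** The omission is real. Model (1) does not index the data that will be collected, and it assumes independence among profiles that share a day. The consequence is possible inefficiency and a 90% CI without assured coverage, not a bias of known direction.

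With an additive day effect, the variance penalty is 2% at a share of 0.1, 6% at 0.2, 15% at 0.3 and 45% at 0.5, with coverage close to nominal on the example table. Up to about 0.2 this is negligible. With day-to-day differences in response per unit dose, coverage falls to about 78% to 88% over the assumed range.

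All of this rests on a table that both documents label an example, on 18 completers spread evenly over the sequences, and on assumed variance components. The change is worth making because it is cheap, but the documents do not show a large loss.

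**What to change.** In SAP 9.4.2, add an index m = 1, 2, 3 for the dose within the day and a random intercept for subject by period:

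Y_klm = β0 + β1 d_klm + β2 d_klm Z_klm + u_k + v_kl + e_klm, with v_kl normal and independent of the other terms.

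Make the same change in the nonlinear form that estimates λ. Drop v_kl only if its variance is estimated at zero; the model then reduces to model (1).

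As a pre-specified sensitivity analysis, either allow a random dose slope by subject-period or report the CI for λ from a variance estimate robust to clustering. If the clusters are subjects, 18 is few and a small-sample correction should be named.

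The cost is one more random-effect line in the model and one more variance component, which may be estimated at zero. No change to design, sampling or sample size is needed. If the sponsor prefers to keep model (1), the SAP should still correct the indexing and justify leaving out within-day correlation.

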### **3.2.1. Clinical Experience**

LY3185643 has been administered SC to 27 healthy subjects as single doses of 0.01 mg, 0.03 mg, 0.05 mg, 0.06 mg, 0.1 mg, 0.2 mg, 0.3 mg, 0.48 mg, and 0.72 mg (n = 3 subjects for each dose level). Preliminary PK data available for doses up to 0.2 mg show dose-dependent increases in LY3185643 exposures. Over the dose range of 0.01 to 0.2 mg, the median time to peak concentrations ranged between 0.5 to 1.25 hours, mean peak concentrations ranged between 0.13 to 4.25 ng/mL, and mean terminal  $t_{1/2}$  ranged between 0.5 to 0.75 hours. LY3185643 concentrations decreased below the limit of quantification by 4 hours postdose. Dose-dependent increases in glycemic response were observed up to 0.2-mg dose level. Maximum mean blood glucose elevations of up to 180 mg/dL were observed at doses above 0.2 mg of LY3185643. Peak glucose concentrations were reached between 0.5 to 2 hours postdose, and glycemic effects lasted for up to 3 hours postdose. This transient glycemic effect at high LY3185643 concentrations is consistent with rGlucagon findings and likely reflects a feedback inhibition of hepatic glucose output in response to exogenous glucagon administration (Mighiu et al. 2013).

Adverse events (AEs) included nausea, vomiting, light headed, headache, dizziness, vasovagal episode, erythema at injection site, loose stools, feeling hot and cold, abrasion of right leg, increased appetite, right thigh ache, drowsiness, feels sleepy, feels faint, decreased alertness, and dehydration. The most common (67% of 36 reported events) AEs were nausea (n=10), vomiting (n=6), headache (n=3), dizziness (n=3), and light headedness (n=2). No serious AEs (SAEs) were noted.

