**Table APCA.5.1. Treatment Sequences**

Cohort a	Treatment Period 1			Treatment Period 2			Treatment Period 3		
A	Dose 1	Dose 9	Dose 7	Dose 6	Dose 4	Dose 8	Dose 5	Dose 3	Dose 2
B	Dose 2	Dose 7	Dose 8	Dose 4	Dose 5	Dose 9	Dose 6	Dose 1	Dose 3
C	Dose 3	Dose 8	Dose 9	Dose 5	Dose 6	Dose 7	Dose 4	Dose 2	Dose 1
D	Dose 4	Dose 6	Dose 2	Dose 3	Dose 9	Dose 1	Dose 8	Dose 7	Dose 5
E	Dose 5	Dose 4	Dose 3	Dose 1	Dose 7	Dose 2	Dose 9	Dose 8	Dose 6
F	Dose 6	Dose 5	Dose 1	Dose 2	Dose 8	Dose 3	Dose 7	Dose 9	Dose 4
G	Dose 7	Dose 1	Dose 4	Dose 9	Dose 2	Dose 6	Dose 3	Dose 5	Dose 8
H	Dose 8	Dose 2	Dose 5	Dose 7	Dose 3	Dose 4	Dose 1	Dose 6	Dose 9
I	Dose 9	Dose 3	Dose 6	Dose 8	Dose 1	Dose 5	Dose 2	Dose 4	Dose 7

Note: This is an example table; subjects will be assigned a treatment sequence according to the actual treatment schedule provided to the site.

Dose assignment: Dose 1 = 10 µg LY3185643; Dose 2 = 25 µg LY3185643; Dose 3 = 50 µg LY3185643; Dose 4 = 100 µg LY3185643; Dose 5 = 200 µg LY3185643; Dose 6 = 10 µg rGlucagon; Dose 7 = 25 µg rGlucagon; Dose 8 = 50 µg rGlucagon; Dose 9 = 200 µg rGlucagon.

a In each cohort, LY3185643 and rGlucagon will be administered.

The Schedule of Activities (Section 2) details the procedures and tests occurring at specific times during the study.

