## 5.2. Number of Participants

Up to 37 subjects may be enrolled so that approximately 18 subjects complete the study.

Subjects who receive all 9 doses of study treatment will be considered as completing the study.

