## **10.3.3. Pharmacodynamic Analyses**

The PD time-action and response of LY3185643 and rGlucagon will be compared to establish the relative potency between LY3185643 and rGlucagon.

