Cohort A	Admit to CRU	Dose	Dose	Dose	Stay Overnight D/C home	The scheme on the left is repeated for Period 2 and Period 3.				
Cohort B		Dose	Dose	Dose						
Cohort C		Dose	Dose	Dose						
Period 2				Period 3						
Day -1				Day 1			Day 2			
Cohort D	Admit to CRU	Dose	Dose	Dose	Stay Overnight D/C home					
Cohort E		Dose	Dose	Dose						
Cohort F		Dose	Dose	Dose						
Period 2				Period 3						
Day -1				Day 1			Day 2			
Cohort G	Admit to CRU	Dose	Dose	Dose	Stay Overnight D/C home					
Cohort H		Dose	Dose	Dose						
Cohort I		Dose	Dose	Dose						

Abbreviations: CRU = clinical research unit; D/C = discharge.

Figure 1.

Approximately 18 subjects are expected to complete the study. Each subject will be randomized to 1 of 9 treatment sequences comprising single SC doses of LY3185643 or rGlucagon (Table 1). Subjects who discontinue may be replaced to target at least 18 completers; the replacement subject will be assigned the treatment sequence of the discontinued subject and complete all 3 treatment periods (total of 9 doses).

Cohort ^a	Treatment Period 1			Treatment Period 2			Treatment Period 3		
A	Dose 1	Dose 9	Dose 7	Dose 6	Dose 4	Dose 8	Dose 5	Dose 3	Dose 2
B	Dose 2	Dose 7	Dose 8	Dose 4	Dose 5	Dose 9	Dose 6	Dose 1	Dose 3
C	Dose 3	Dose 8	Dose 9	Dose 5	Dose 6	Dose 7	Dose 4	Dose 2	Dose 1
D	Dose 4	Dose 6	Dose 2	Dose 3	Dose 9	Dose 1	Dose 8	Dose 7	Dose 5
E	Dose 5	Dose 4	Dose 3	Dose 1	Dose 7	Dose 2	Dose 9	Dose 8	Dose 6
F	Dose 6	Dose 5	Dose 1	Dose 2	Dose 8	Dose 3	Dose 7	Dose 9	Dose 4
G	Dose 7	Dose 1	Dose 4	Dose 9	Dose 2	Dose 6	Dose 3	Dose 5	Dose 8
H	Dose 8	Dose 2	Dose 5	Dose 7	Dose 3	Dose 4	Dose 1	Dose 6	Dose 9
I	Dose 9	Dose 3	Dose 6	Dose 8	Dose 1	Dose 5	Dose 2	Dose 4	Dose 7

Note: This is an example table; subjects will be assigned a treatment sequence according to the actual treatment schedule provided to the site.

Dose assignment: Dose 1 = 10 µg LY3185643; Dose 2 = 25 µg LY3185643; Dose 3 = 50 µg LY3185643;
Dose 4 = 100 µg LY3185643; Dose 5 = 200 µg LY3185643; Dose 6 = 10 µg rGlucagon; Dose 7 = 25 µg
rGlucagon; Dose 8 = 50 µg rGlucagon; Dose 9 = 200 µg rGlucagon.

^a In each cohort, LY3185643 and rGlucagon will be administered.

Table 1.

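### If glucose response is concave in dose, the 100 µg dose given only for LY3185643 pulls the SAP's straight-line conversion factor below 1 for equally potent drugs

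*SAP*

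**What the plan says.** Protocol 10.3.3 states the aim: the time-action and response of the two drugs "will be compared to establish the relative potency between LY3185643 and rGlucagon". Protocol 3.1 says the result will guide changes to artificial-pancreas control algorithms.

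The dose sets differ (Protocol Table APCA.5.1; same list in SAP 5). After 10, 25 and 50 µg, the LY3185643 list continues "Dose 4 = 100 µg LY3185643; Dose 5 = 200 µg LY3185643". The rGlucagon list is "Dose 6 = 10 µg rGlucagon; Dose 7 = 25 µg rGlucagon; Dose 8 = 50 µg rGlucagon; Dose 9 = 200 µg rGlucagon", with no 100 µg level. A completer receives all nine doses ("Completers are defined as subjects who have received all 9 doses").

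For each PD parameter, SAP 9.4.2 fits Y = β0 + β1·d + β2·d·Z plus a random subject effect. Dose d is untransformed, in mg, and Z = 1 for LY3185643. The intercept is common to both drugs: "There is no term for the treatment group indicator". The conversion factor is λ = β1/(β1 + β2), reported with a 90% CI, and λ below 1 means LY3185643 looks more potent.

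SAP 9.4.2 plans no linearity check and no alternative curve. SAP 9.3.2 does specify a lack-of-fit test for the PK power model.

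**The concern.** Equal potency means that both drugs share one dose-response curve. What model (1) compares is two fitted slopes, taken over two different dose sets. These are the same comparison only if the curve is a straight line. On a concave curve the true mean at 100 µg lies above the fitted line, and only LY3185643 has data there. Its slope is pulled up, β2 becomes positive and λ falls below 1, although the drugs do not differ.

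At stake is the number meant to translate rGlucagon dosing logic to LY3185643. A reported potency difference could come from the choice of doses. The scenario matters because Protocol 5.5 expects the two potencies to be similar.

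**Working it through.** **Inputs.** Doses and model as above. Eighteen completers (Protocol 5.2: "Up to 37 subjects may be enrolled so that approximately 18 subjects complete the study"). The documents give neither the curve shape over 10-200 µg nor the within-subject SD, so both are assumed over a range. They also state no expected λ or precision target, so there is no plan figure to reproduce.

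**1. SAP algebra.** Setting β0 + (β1+β2)D1 = β0 + β1·D0 gives D1 = [β1/(β1+β2)]·D0, and β2 = β1(1−λ)/λ. Both forms in the SAP are correct.

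**2. How each dose enters β2.** With every subject receiving all nine doses, the mixed-model slopes equal least squares over the nine cells. When both drugs follow the same curve f, the cell weights on β2 add up by dose to:

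| Dose (µg) | 10 | 25 | 50 | 100 | 200 |
|---|---|---|---|---|---|
| Weight | −0.318 | −0.353 | −0.411 | +1.838 | −0.756 |

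The weights sum to zero. So do weight × dose in mg: −0.0032 − 0.0088 − 0.0206 + 0.1838 − 0.1512 = 0.000. A linear curve therefore gives β2 = 0 and λ = 1. Only 100 µg has positive weight.

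**3. Worked case: Emax, ED50 50 µg, f(d) = d/(d + 50).** The values are 0.1667, 0.3333, 0.5, 0.6667 and 0.8.

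β2 = −0.0530 − 0.1177 − 0.2055 + 1.2253 − 0.6048 = 0.2443. The same fit gives β0 = 0.2510 and β1 = 2.8565, so λ = 2.8565/(2.8565 + 0.2443) = 0.921. At 0.1 mg the rGlucagon line is 0.2510 + 0.2857 = 0.5367, below the true 0.6667.

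**4. Other curves, identical drugs.**

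| Curve | λ, all doses | λ, without 100 µg |
|---|---|---|
| Linear | 1.000 | 1.000 |
| Emax, ED50 25 / 50 / 100 / 200 µg | 0.908 / 0.921 / 0.939 / 0.958 | 1.000 |
| Square root | 0.964 | 1.000 |
| Linear to a plateau at 100 µg | 0.848 | 1.000 |
| Convex, d^1.5 | 1.034 | 1.000 |

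Any increasing concave curve is a straight line plus a positive mix of hinges min(d, c). β2 is positive for every hinge c between 10 and 200 µg, and the lowest λ is about 0.848. Adding 9 to 19 early dropouts moves λ by less than 0.005 for the Emax and square-root curves checked.

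**5. The 90% CI.** Simulation used 18 completers, identical drugs and a delta-method interval with t on 17 df (an assumption; the SAP does not say how the interval is formed). SD is a share of the 200 µg response.

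| SD | CI excludes 1, Emax ED50 25-200 µg |
|---|---|
| 10% | about 23% to 33% |
| 15% | about 18% to 24% |
| 20% | about 15% to 20% |
| 30% | about 12% to 15% |

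The square-root curve gives about 18% at SD 10%. A linear response gives about 8%. Almost all Emax exclusions lie below 1, where the nominal rate is 5%. Matched doses give 1% to 8% in total.

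**6. When potencies truly differ (ED50 50 µg).**

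| True λ | All-dose λ | Matched-dose λ |
|---|---|---|
| 0.50 | 0.692 | 0.767 |
| 0.80 | 0.837 | 0.915 |
| 1.25 | 1.021 | 1.099 |

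At true λ 0.80 and SD 10%, the 90% CI misses the truth in about 4% of trials with all doses and 57% with matched doses.

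**The case against.** The strongest objection is to matched doses as a remedy. They give λ = 1 only when the drugs are equally potent. With a concave curve and a more potent LY3185643, the matched fit is further from the truth than the SAP's own fit, which benefits from offsetting errors (step 6). A reader might infer that dropping 100 µg yields an unbiased λ and should replace the planned estimate. The calculations do not support that: under curvature neither straight-line λ is calibrated away from 1. The low matched-dose exclusion rates also partly reflect lack of fit inflating the residual variance. This objection stands and shapes the fix.

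A second objection is that concavity is not documented. Protocol 3.2.1 says "Dose-dependent increases in glycemic response were observed up to 0.2-mg dose level", which spans the whole studied range and is compatible with little curvature. Its mention of feedback inhibition concerns high concentrations, so it supports flattening only indirectly. This also stands: a reader might infer that LY3185643 will be reported as more potent, but the documents support only the conditional statement. The SAP also sets no test of λ = 1 and no decision threshold.

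Third, the absent treatment main effect might be read as the fault. It is not: the same common-intercept model gives λ = 1 for identical drugs on matched doses.

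Protocol 10.3.3.2 allows PD parameters to be transformed if needed, but names no transformation or trigger, so it does not answer the point.

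**Conclusion.** The concern holds conditionally. If a PD parameter rises concavely over 10-200 µg, model (1) with the planned doses gives an expected λ below 1 for equally potent drugs. The shortfall is about 4% to 9% for the Emax curves tabulated and at most about 15% for any increasing concave curve. The rate of falsely excluding 1 depends strongly on the assumed SD.

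This is an expected value; a single trial can still give λ above 1. The point applies to parameters that increase with dose, such as glucose Cmax and incremental AUC, and not necessarily to tmax. The cause is a straight line fitted over unmatched doses with no planned check of shape. It is worth correcting because the error has a predictable direction under concavity and guarding against it needs no new data.

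**What to change.** In SAP 9.4.2:

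- Keep the all-dose fit. Add the same model fitted to the doses common to both drugs (10, 25, 50 and 200 µg), and report both λ values with 90% CIs side by side.
- State that any claim of unequal potency rests on the matched-dose fit. Do not make the matched-dose λ the sole lead estimate.
- Add a PD lack-of-fit check modelled on SAP 9.3.2: enter the nine-level dose group after d and d·Z, which leaves 9 − 3 = 6 df. If linearity fails, report λ from a curved model with a common shape, for example Emax with the LY3185643 dose entered as d/λ. A passed check does not prove linearity, so report both straight-line fits in any case.
- Keep the 100 µg data in all summaries and profiles.

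Protocol 10.3.5 says the sponsor's team is unblinded and may analyse data during the trial, so the wording should be dated before any λ is computed.

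Cost: SAP text and one extra model run per parameter, plus the curved model if needed. Under linearity the matched-dose SE is about 5% larger (0.061 to 0.064 at SD 20%). The larger cost is power: at true λ 0.80, ED50 50 µg and SD 20%, the CI falls below 1 in about 20% of trials with matched doses against 60% with all doses, though part of that 60% is the bias itself.
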